## 7 Prospective Feasibility Study Procedures and Assessments

#### 7.1 **Pre-enrolment**

Patients will be identified for potential study participation at routine outpatient clinics, lung or pleural MDTs, inpatient reviews or LAT sessions.

#### 7.2 Eligibility Assessment and Consent

Patients identified as meeting the initial eligibility criteria will be approached by a member of the research team at their first clinic appointment following diagnosis of BAPE (after CT or biopsy if indicated) and provided with a study PIS –'Visit 1'. Visit 1

can also be completed during an inpatient stay, if required. Patients with a radiological diagnosis of BAPE can also be recruited from clinics at any stage in their follow up if they meet inclusion/exclusion criteria.

Eligibility will be documented by a medially qualified member of the team prior to registration and written consent being sought. Sufficient time will be given for the patient to consider involvement and to have any questions relating to the study answered. If the patient would like more time to consider their involvement, a member of the research team will contact discuss this at a later date. Screened patients will be recorded as on a Screening Log.

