#### 4.4.2 **Prospective Study End-points**

The **Primary End-point** shall be Feasibility, defined as the ability to recruit 27 patients from 4 centres over 12-months (or 14 patients over any 6-month period) meeting the following criteria:

- a) They satisfy all Meso-ORIGINS eligibility criteria (see below)
- b) They deem the proposed thoracoscopic surveillance program acceptable (see *4.4.2.1 Patient Acceptability* below)
- c) Their study team deem that at least one LAT at/before 6 months is technically feasible (see *4.4.2.2 LAT Technical Feasibility* below)

This recruitment rate is equivalent to 6.8 patients/centre/year, based on the assumptions that 850 patients will be required for adequate signature differentiation in Meso-ORIGINS and 25 centres will recruit (similar to the DIAPHRAGM study (3)) over 5 years.

It is not considered ethical to directly test feasibility by fully executing the proposed surveillance protocol until the study has proven deliverable, particularly with regard to sample size (*see Retrospective Cohort Study*). Therefore, patient acceptability and technical feasibility will be assessed indirectly.

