### 5.1.2 Diagnosis of Incident MPM

Contrast enhanced computed tomography (CT) remains the key radiological investigation for suspected pleural malignancy (PM), including MPM. (12) Features of pleural malignancy visible on CT include more than one centimetre of pleural thickening, nodular or mediastinal pleural thickening, inter-lobar fissural modularity and infiltration of the chest wall or diaphragm (13, 14). However, results from a recent study suggested that almost half of patients with an eventual diagnosis of pleural malignancy have a benign CT. (15) Therefore, a benign CT report should not be used alone in confirming a non-malignant diagnosis.

The diagnostic yield of fluid cytology in malignant pleural effusion is approximately 60%, varying by tumour type (12). However, this is significantly lower in MPM, due to the bland cytological appearance of MPM cells, making it difficult to differentiate MPM from benign reactive mesothelial proliferation. This is reflected in the recommendations made in the recent BTS guidelines for MPM, which recommends histological confirmation of all cases. (16)

Local Anaesthetic Thoracoscopy (LAT) allows direct visualisation of abnormal areas of pleura, multiple biopsies to be taken and provision of definitive pleural effusion management, e.g. pleurodesis, within a single procedure. LAT is well-tolerated and can be performed as a day-case. It offers high diagnostic sensitivity (MPM sensitivity 92.6%, specificity 100% n=1369 cases) and is associated with a low complication rate (0% mortality in over 2000 diagnostic LAT cases across 28 studies and a 1.8% major complication rate in over 4500 LAT cases across 47 studies). (17)

Thoracic ultrasound (TUS) is necessary to assess the pleural space characteristics prior to LAT. During respiration, the parietal pleural slides on the visceral pleural, producing the 'sliding sign'. This would not be present if there was pleural adherence, previous pneumothorax or previous pleurodesis. Therefore, the presence of the 'sliding sign' can be used to assess LAT feasibility. TUS can also identify potential challenges to thoracoscopy such as pleural thickening and septation. (8) In cases where LAT is not feasible because either the patient is frail, pleural fluid is heavily located, or where the lung is adherent to the chest wall, TUS-directed cutting pleural biopsy should be considered as an alternative (9).

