# 6 Patient Selection

#### 6.1 Inclusion Criteria

All study participants involved in either the Prospective Feasibility Study or the Retrospective Cohort Study will be subject to the following inclusion criteria:

- History of asbestos exposure or compatible radiology, e.g., pleural plaques
- CT imaging compatible with BAPE (which must include pleural effusion) or compatible histological diagnosis at biopsy including any of the following: benign fibrinous pleurisy, non-specific pleuritis or atypical mesothelial proliferation

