#### NB Histological confirmation is required for the Retrospective Cohort Study

Patients recruited to the Prospective Feasibility Study must also meet the following additional inclusion criteria:

- Informed written consent
- Expected prognosis  $\geq$  6 months

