#### 7.4 Study Visits

#### 7.4.1 Visit 1

Visit 1 activities will occur at clinic appointment following biopsy or at any stage in follow up of radiological diagnosis of BAPE cases.

Visit 1 activities will include:

- Provision of Patient Information Sheet
- Confirmation of eligibility by a medically qualified team member
- Documentation of informed written consent (medically qualified team member not required)
- Registration of patient by email ([contact])
- Completion of Baseline CRF, which will include the following data:

Demographics	Age*, Gender
Asbestos Exposure History	Occupation Period of employment Job Type & Code** Indirect exposure details
CT Findings*	
 
Benign or Malignant Features
 
Based on previously reported criteria (9,15)
 
Calcified Pleural plaques
 
Present or Not Present
 

CXR appearance*	Effusion Laterality

	Effusion Size: • Small effusion (<50% thorax) • Large effusion (≥50% thorax)
LAT details (if applicable)	
 
Were adequate views obtained?
 
Which surfaces were abnormal?
 
What was the nature of the abnormality/ies?
 
Smooth
 
Macro-nodular
 
Micro-nodular
 
Number of biopsies
 
Did the lung prove non-expansile (based on BTS criteria (≥50% reapposition) (19)
 
Did the subject have pleurodesis?
 
Did the subject have an IPC placed?
 
Histology, Cytology, Pleural Fluid Chemistry Results
 

\*at presentation

\*\*Job type options and codes available in CRF

#### 7.4.2 Visit 2

Visit 2 should coincide with a clinic visit approximately 6 months after Visit 1. However, Visit 2 activities can be completed 2 weeks earlier or later than 6 months following biopsy if the patient presents with symptomatic recurrence of pleural effusion or any other manifestation of progressive ipsilateral pleural disease (in the judgment of the site PI). If patient recruited ≥6months after initial BAPE diagnosis then visit 1 and 2 can be combined on Visit 1.

Visit 2 activities will include:

- History and examination
- Completion of Patient Acceptability Questionnaire
- Thoracic Ultrasound for assessment of LAT Feasibility based on thoracic ultrasound markers (8). Technical feasibility of LAT will be defined as either:
   o sufficient pleural fluid to allow safe LAT access or
  - sufficient lung-sliding to allow pneumothorax induction prior to LAT

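### The feasibility target is a yearly rate projected over 5 years, but CT-diagnosed patients already under follow-up when a centre opens count towards it like new cases

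*Protocol*

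**What the plan says.** Protocol Section 4.4.2 gives the primary end-point as feasibility, "defined as the ability to recruit 27 patients from 4 centres over 12-months (or 14 patients over any 6-month period"), among patients who are eligible, find the thoracoscopic programme acceptable and are judged technically suitable for LAT. It explains the threshold: "This recruitment rate is equivalent to 6.8 patients/centre/year", on the assumption that "850 patients will be required for adequate signature differentiation in Meso-ORIGINS and 25 centres will recruit" over 5 years.

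The rules on who can be counted are these:

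- Section 6.1 admits patients with "CT imaging compatible with BAPE (which must include pleural effusion) or compatible histological diagnosis at biopsy".
- Section 7.2 makes the first clinic appointment after diagnosis the usual point of approach, then adds: "Patients with a radiological diagnosis of BAPE can also be recruited from clinics at any stage in their follow up". Section 7.4.1 repeats this for Visit 1. Neither limits the time since diagnosis.
- Section 7.4.2 says: "If patient recruited ≥6months after initial BAPE diagnosis then visit 1 and 2 can be combined on Visit 1". Section 7.7 has the same rule.
- Section 10.2.1 treats the end-point as met when LAT is acceptable and technically feasible at Visit 2. Date and method of diagnosis play no part.

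For the retrospective cohort, which is meant to refine the 850, the note under Section 6.1 says: "Histological confirmation is required for the Retrospective Cohort Study".

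**The concern.** The threshold is a flow: so many patients per centre per year, repeated for 5 years. Patients already in follow-up clinics when a centre opens are a stock, and a centre can draw on that stock once. The end-point adds the two together.

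Two features make the mixture matter more. A patient 6 months or more past diagnosis can be assessed on day 0, whereas a newly diagnosed patient is normally assessed about 6 months after Visit 1. Also, the shorter limb needs only 14 patients in any 6-month window, so a cluster of existing patients soon after opening could supply much of it.

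What is at stake is the study's main conclusion. A result of feasible is meant to show that 25 centres can recruit 850 patients in 5 years. If part of the count cannot recur, it does not show that.

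A related point concerns population. The 12% transition rate behind the 850 comes from BAPE found among LAT patients (Section 5.1.3), and the retrospective cohort requires histology. Prospective recruitment also accepts CT alone. Recruitment speed and transition rate are then measured in groups that only partly overlap, although Meso-ORIGINS planning needs both.

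**Working it through.** **The plan's own figures**

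- Required rate (Section 4.4.2): 850 / (25 × 5) = 6.8 per centre per year. For 4 centres, 4 × 6.8 = 27.2 per year (stated 27) and 13.6 per half-year (stated 14). These reproduce.
- Supply (Section 10.1.1): 120 to 200 LATs × 30% = 36 to 60 BAPE cases (stated 40 to 60). At the stated maximum of 50% feasible, that gives 18 to 30. New LAT cases alone reach 27 only if there are at least 27 / 0.5 = 54 of them, near the top of the range. The CT-only route is not in this estimate, so it could decide the result.

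**Effect of a backlog on the 12-month limb**

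Let B be the number among the 27 who were diagnosed before their centre opened. The protocol gives no value for B, so a range is shown. Three assumptions apply: new cases continue at the observed rate, backlog is recruited once, and each of the 25 future centres has the same average backlog of B/4.

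- New-case rate per centre per year = (27 − B)/4
- 5-year yield = 25 × 5 × (27 − B)/4 + 25 × B/4 = (25/4)(B + 5(27 − B))
- Years to reach 850 = (850 − 6.25B) / (6.25(27 − B))

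| B (assumed) | New cases per centre per year | 5-year yield | Short of 850 | Years to 850 |
|---|---|---|---|---|
| 0 | 6.75 | 844 | 1% | 5.0 |
| 6 | 5.25 | 694 | 18% | 6.2 |
| 12 | 3.75 | 544 | 36% | 8.3 |
| 18 | 2.25 | 394 | 54% | 13.1 |

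The formula simplifies to 6.25 × (135 − 4B), so each backlog patient among the 27 takes 25 off the 5-year yield. The end-point is met in every row.

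**Effect on the 6-month limb**

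Fourteen in 6 months projects to (14 × 2/4) × 125 = 875. With B backlog patients among the 14, the yield is (2(14 − B)/4) × 125 + (B/4) × 25. This gives 650 for B = 4, 481 for B = 7 and 313 for B = 10. A given B costs more here because the 6-month count is doubled to give a yearly rate.

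**Whether another rule already prevents this**

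Consecutive invitation (Sections 6.3 and 6.6) governs the order of approach, not the date of diagnosis. Section 7.3 bars screening and registration before site activation, but not patients diagnosed before it. Neither separates new from existing patients.

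**The case against.** The strongest reply is that no inflation has been shown. B is not in the protocol, and with B = 0 the projection is 844, essentially on target. The usual route is approach at the first appointment after diagnosis, and the sample size of 54 is justified from new LAT cases only. Entry at any stage also covers CT patients diagnosed after opening but not enrolled at their first visit, and they are not backlog. All of this stands. It limits the claim to what the counting rule permits, and it does not remove the gap in the rule.

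A reader might infer three stronger conclusions, which the protocol does not support:

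- **That the rate is certainly overstated.** The size is unknown, and the direction is not assured. Long-standing patients may less often be technically feasible, and they would still use places under the cap of 54, which could lower the feasible count.
- **That patients first assessed long after diagnosis cannot meet criterion (c).** Section 4.4.2 gives no starting point for its 6-month limit. Visit 2 is timed mainly from Visit 1, and on that clock a day-0 assessment is within the limit. The undefined origin is a separate, smaller ambiguity.
- **That CT-only patients should not count.** They meet the eligibility criteria that the end-point cites. Section 5.1.2 does say that "a benign CT report should not be used alone in confirming a non-malignant diagnosis", but that concerns diagnostic certainty and says nothing about recruitment speed. The mismatch with the biopsy-based transition rate calls for a split in reporting, not exclusion.

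A last objection concerns the remedy. Counting only new patients against a fixed 27, while recruitment still stops at 54, could create a false failure. If 12 of the 54 were existing patients, at most (54 − 12) × 50% = 21 new ones could count. This is right, and it is why the comparison should use a rate per centre-year. Breakdowns of results can be left to a statistical analysis plan, but what counts towards the primary end-point is fixed in this protocol.

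**Conclusion.** The point holds as a defect in the counting rule. As written, the end-point can be declared met on a count that mixes a one-off stock with a yearly flow, and that count cannot then be read as 6.8 per centre per year for 5 years. The consequence ranges from none (B = 0, yield 844) to a shortfall of 18%, 36% or 54% for B = 6, 12 or 18. The 6-month limb is the more exposed of the two.

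These sizes rest on an assumed B, a constant new-case rate and equal average backlog at future centres. They show what the rule would allow and do not predict what will happen. The rule should be changed, because the change is cheap and determines what the study can conclude.

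**What to change.** Leave eligibility, enrolment and visits unchanged. In Sections 4.4.2 and 10.2.1:

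1. Base the rate compared with 6.8 per centre per year on feasible patients first diagnosed with BAPE after their centre opened, divided by centre-years of open recruitment. Early closure at 54 then shortens the denominator too. In the example above, 21 new feasible patients from 4 centres still reach 6.8 if recruitment was open for no more than 21 / (4 × 6.8) = 0.77 years. Apply the same rule to the 6-month limb.
2. Report feasible patients diagnosed before opening separately, and add them once per centre to the 5-year projection.
3. Report the rate by histology-confirmed and CT-only diagnosis, so that it can be set beside the biopsy-based transition rate. CT-only patients remain eligible and counted.

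The costs are modest. The headline count may be smaller. The baseline CRF items listed in Section 7.4.1 include no date of BAPE diagnosis, so date and method of diagnosis need to be recorded. CT-only cases need a defined date, because Section 8 defines it only by the pathology report, and only for the retrospective study.

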### 7.3 Registration

Patients cannot be screened or registered to the trial until the site has been activated to begin recruitment. All study participants should be registered after Eligibility Assessment. Registration requires an email to be sent to the following address.

#### [contact]

A study number will be sent by return email to the site within the same working day. The patient is considered to be registered once a registration email has been sent.

#### 7.4 Study Visits

#### 7.4.1 Visit 1

Visit 1 activities will occur at clinic appointment following biopsy or at any stage in follow up of radiological diagnosis of BAPE cases.

Visit 1 activities will include:

- Provision of Patient Information Sheet
- Confirmation of eligibility by a medically qualified team member
- Documentation of informed written consent (medically qualified team member not required)
- Registration of patient by email ([contact])
- Completion of Baseline CRF, which will include the following data:

Demographics	Age*, Gender
Asbestos Exposure History	Occupation Period of employment Job Type & Code** Indirect exposure details
CT Findings*	
 
Benign or Malignant Features
 
Based on previously reported criteria (9,15)
 
Calcified Pleural plaques
 
Present or Not Present
 

CXR appearance*	Effusion Laterality

	Effusion Size: • Small effusion (<50% thorax) • Large effusion (≥50% thorax)
LAT details (if applicable)	
 
Were adequate views obtained?
 
Which surfaces were abnormal?
 
What was the nature of the abnormality/ies?
 
Smooth
 
Macro-nodular
 
Micro-nodular
 
Number of biopsies
 
Did the lung prove non-expansile (based on BTS criteria (≥50% reapposition) (19)
 
Did the subject have pleurodesis?
 
Did the subject have an IPC placed?
 
Histology, Cytology, Pleural Fluid Chemistry Results
 

\*at presentation

\*\*Job type options and codes available in CRF

#### 7.4.2 Visit 2

Visit 2 should coincide with a clinic visit approximately 6 months after Visit 1. However, Visit 2 activities can be completed 2 weeks earlier or later than 6 months following biopsy if the patient presents with symptomatic recurrence of pleural effusion or any other manifestation of progressive ipsilateral pleural disease (in the judgment of the site PI). If patient recruited ≥6months after initial BAPE diagnosis then visit 1 and 2 can be combined on Visit 1.

Visit 2 activities will include:

- History and examination
- Completion of Patient Acceptability Questionnaire
- Thoracic Ultrasound for assessment of LAT Feasibility based on thoracic ultrasound markers (8). Technical feasibility of LAT will be defined as either:
   o sufficient pleural fluid to allow safe LAT access or
  - sufficient lung-sliding to allow pneumothorax induction prior to LAT
- Recording of any new pleural diagnosis and/or the results of any further imaging or sampling tests

#### 7.5 Trial Images

All CXR and CT images relating to trial participation will be securely stored on NHS PACS systems in line with routine clinical practice.

#### 7.6 End of Trial

Trial recruitment will terminate after 54 patients have been recruited, after 27 patients have been met the primary end-point regarding feasibility, or 12 months after the study opens, whichever is soonest. The trial will end once the final patient recruited has completed their 2-6 month follow up visit (Visit 2).

### 7.7 Schedule of Assessments

Visit Number	1	2
Approximate timing	Day 0 (Recruitment)	6 months* (+/-2weeks)
Clinical Activity		
Clinical review	x	х
Chest Radiograph	x	х
Thoracic ultrasound	x	х
Study Activity		
Review Eligibility Criteria** and complete eligibility assessment form	X	
Introduce study if eligible	x	
Provide with PIS	x	
Opportunity for discussion	x	
Informed written consent	X †	
Register patient with CTU by email	X †	
Complete Baseline CRF	x†	
Complete Follow-up CRF, including technical feasibility of LAT based on Ultrasound findings		Х
Complete Patient Acceptability Questionnaire		х

\* Visit 2 can occur as early as 2 month following date of biopsy if patient presents with symptomatic recurrence of pleural effusion or any other manifestation of progressive ipsilateral pleural disease (in the judgment of the site PI). If patient recruited  $\geq$ 6months after initial BAPE diagnosis then visit 1 and 2 can be combined at day 0.

\*\* Eligibility for the study must be confirmed by a medically qualified member of the research team. Consent may be documented by a non-medically qualified team member.

+ If the patient wishes more time to consider participation in the study, these activities may occur at a subsequent research visit arranged by a member of the research team.

# 8 Retrospective Study Data Collection and Recording

The following data will be recorded retrospectively for all eligible patients using LAT/VAT/image guided biopsy databases and electronic health records at the study centres. A data collection form (.x/s) will be provided, including pre-populated study IDs. All data will be recorded in a linked anonymised format.

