### 4.5.2 Retrospective Cohort Study End-points

The **Primary End-Point** shall be the rate of MPM transition, defined as the number of eligible patients diagnosed with MPM within 2 years of the index diagnosis of BAPE divided by the total number of eligible patients.

The **Secondary End-Point** shall be a logistic regression model for MPM transition using baseline data as predictors.

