#### 6.2 Exclusion Criteria

All study participants involved in either the Prospective Feasibility Study or the Retrospective Cohort Study will be subject to the following exclusion criteria:

- Histological diagnosis of MPM or any secondary pleural malignancy
- Diagnosis of pleural infection, empyema or granulomatous pleuritis

In addition, potential cases identified for the Retrospective Cohort Study must also be assessed against the following **additional exclusion criterion:** 

• < 2 years follow-up completed at the point of enrolment

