### 6.4 Retrospective Cohort Study Case Identification

Electronic databases will be used to identify cases meeting the study eligibility criteria. Existing databases in the trial centres involved contain data on approx. 1000 patients that have undergone LAT. These database should contain approx. 300 cases of BAPE based on previously published BAPE incidence of 30% in this population (2). Existing databases from VATS and image guided biopsy cases will also be used.

Cases can be entered throughout the period that the study is open. This includes cases diagnosed with BAPE with less than 2 years follow-up at the point the study opens, so long as 2 years follow-up has concluded by the time they are enrolled. The retrospective study will end after 12 months from opening and therefore patients who had a diagnosis of BAPE following LAT on or before 31/11/17 could be recruited.

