#### 6.6 Bias Reduction

In the retrospective study there is potential for recall and omission bias in data collection. We expect that this will be minimal as each centre that will be collecting data will have prospective databases where all LAT/VATS/image guided biopsies are recorded. In the prospective feasibility study there will be consecutive multicentre recruitment which will improve generalisation to a UK population. This is important as the data gathered will ultimately be used in the design of a future larger study.

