# The date of BAPE diagnosis will be recorded. This is defined as the date on the pathology report describing features of BAPE that meet they eligibility criteria as explained in section 6.

Imaging, pleural fluid and blood results should be recorded at first presentation.

Cases can be entered throughout the period that the study is open. This includes cases diagnosed with BAPE with less than 2 years follow-up at the point the study opens, so long as 2 years follow-up has concluded by the time they are enrolled.

Demographics	Age*, Gender
Asbestos Exposure History	Occupational or environmental Nature of Occupation
CT Findings*	
 
Benign or Malignant Features
 
Based on previously reported criteria (5,11)
 
Calcified Pleural plaques
 
Present or Not Present
 

CXR appearance*	Effusion Laterality Effusion Size: • Small effusion (<50% thorax) • Large effusion (≥50% thorax)
Blood Tests*	Haemoglobin Neutrophils Lymphocytes Platelets CRP Albumin LDH Total Protein

Pleural Fluid	Total protein Albumin LDH Glucose Colour Cytology
LAT/VATS Findings	Date index procedure performed Were adequate views obtained? Which surfaces were abnormal? What was the nature of the abnormality/ies? • Smooth • Macro-nodular • Micro-nodular Number of biopsies Did the lung prove non-expansile (based on BTS criteria (≥50% re-apposition) (20) Did the subject have pleurodesis? Did the subject have an IPC placed? Histology, Cytology, Pleural Fluid Chemistry Results
Follow-up Data	Record any new pleural diagnosis since LAT/VATS Record whether MPM diagnoses within 2 years of index LAT/VATS date

\*at presentation

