#### **10.2.2** Retrospective Cohort Study

Results will be reported using simple descriptive statistics. The **primary end-point** shall be the rate of MPM transition. This will be calculated by dividing the number of eligible patients diagnosed with MPM within 2 years of the index diagnosis of BAPE by the total number of eligible patients. The **secondary end-point** shall be based on the content of a logistic regression model for MPM transition generated using baseline data as candidate predictors.

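### The retrospective 2-year MPM rate rests on outcomes found in the study centres' own records, with 'follow-up completed' undefined and no last-known status or death date listed, so missed or dropped patients can bias it unseen

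*Protocol*

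**What the plan says.** - **Outcome source.** Protocol section 8 says the retrospective data will be recorded "using LAT/VAT/image guided biopsy databases and electronic health records at the study centres". No source outside the centres is named.
- **Outcome items.** The Follow-up Data row in section 8 has two entries: any new pleural diagnosis since the procedure, and "Record whether MPM diagnoses within 2 years of index LAT/VATS date". The list has no date last seen or last known MPM-free, no vital status and no entry for unknown status.
- **End-point.** Section 4.5.2 gives this definition of the rate: "number of eligible patients diagnosed with MPM within 2 years of the index diagnosis of BAPE divided by the total number of eligible patients". Section 10.2.2 repeats it.
- **Follow-up rule.** Section 6.2 excludes retrospective cases with "< 2 years follow-up completed at the point of enrolment", and the synopsis gives the same rule as an inclusion criterion. Section 6.4 admits recent cases "so long as 2 years follow-up has concluded by the time they are enrolled", and section 8 repeats this. Section 6.4 then reasons from the length of the study: "therefore patients who had a diagnosis of BAPE following LAT on or before 31/11/17 could be recruited".
- **Bias statement.** Section 6.6 expects recall and omission bias to be minimal because "each centre that will be collecting data will have prospective databases where all LAT/VATS/image guided biopsies are recorded".

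**The concern.** The term on which the end-point depends, completed follow-up, has two possible meanings, and each leads to a different problem.

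If it means that two years have passed since diagnosis, nothing shows that anyone observed the patient during that time. A patient whose care moved elsewhere after the index biopsy, or whose MPM was diagnosed at another hospital, stays in the denominator without an event unless the centre's records happen to show it. If it means documented observation, patients who died or left before two years are removed. That is a selection, and it is harmless only if loss is unrelated to MPM.

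The assurance in section 6.6 concerns something else. A complete log of biopsies protects the finding of index cases, and of repeat biopsies at the same centre. It does not cover MPM diagnosed elsewhere or without a biopsy at the centre.

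The rate matters because it is meant to firm up the Meso-ORIGINS sample size, and the synopsis and section 5.2 both say that a lower rate could make that study unfeasible.

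**Working it through.** **1. The plan's own figures.** Inputs: 850 patients, 12% transition, about 100 MPM cases (synopsis); 25 centres over 5 years (section 4.4.2).
- 850 × 0.12 = 102, and 100 / 0.12 = 833. The plan's 850 is consistent with this.
- 850 / (25 × 5) = 6.8 patients per centre per year, as stated.

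**2. Sampling precision.** With 300 patients and 36 events (12%), the Wilson 95% interval is about 8.8% to 16.2%.

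**3. Elapsed-time reading.** Assumptions, none of them from the documents: true 2-year rate 12%; constant hazard; a share f of patients leaves the centre's view; MPM arising in them afterwards is not seen.

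- Hazard: h = −ln(0.88) / 2 = 0.0639 per year.
- Leaving uniformly over 2 years: the mean share of events still seen among leavers is 1 − (1 − e^(−2h)) / (2h) = 1 − 0.12 / 0.1278 = 0.0613. Observed rate = (1 − f) × 0.12 + f × 0.0613.
- Leaving straight after the biopsy: observed rate = 0.12 × (1 − f).
- Main-study size = 100 / observed rate; per centre per year = size / 125.

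| Scenario | Observed rate | Size for 100 cases | Per centre per year |
|---|---|---|---|
| No loss | 12.0% | 833 | 6.7 |
| f = 20%, uniform | 10.8% | about 924 | 7.4 |
| f = 40%, uniform | 9.65% | about 1,036 | 8.3 |
| f = 10%, immediate | 10.8% | about 926 | 7.4 |
| f = 20%, immediate | 9.6% | about 1,042 | 8.3 |

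**4. Observed-follow-up reading.** Leavers are excluded. Let k be their MPM risk relative to the cohort average. Estimated rate = 0.12 × (1 − f × k) / (1 − f).
- k = 1: 12.0% for any f, so no bias.
- k = 1.5: f = 10% gives 0.102 / 0.90 = 11.3%; f = 20% gives 0.084 / 0.80 = 10.5%.
- With k below 1 the formula gives a rate above 12%, so on this reading the direction is not fixed.

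**5. Which reading the text favours.** Section 6.4 derives recruitability from a calendar date, which points to elapsed time. Section 5.1.1 gives a median MPM survival of 9.5 months. A literal demand for two years of observation would therefore remove many patients who developed MPM and died within the window, and these are numerator cases. Both points favour elapsed time, but neither is a definition.

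**The case against.** The strongest reply is that the follow-up exclusion already settles the matter: a patient who left before two years has not completed follow-up, is ineligible, and so cannot be counted as a non-transition. The date in section 6.4 may mark only the latest admissible diagnosis, without replacing that criterion. This stands to the extent that a reader who infers that the rate is certainly biased downwards goes further than the documents allow. That conclusion needs the elapsed-time reading, or an MPM diagnosis made outside the centre's view in a patient still counted as followed. It does not remove the problem, because the observation reading replaces misclassification with selection.

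Other points also stand. The data collection spreadsheet is not in the documents, so its response codes are unknown; only the listed items can be judged. The reach of the electronic records is not stated, and they may hold letters from other hospitals or notices of death. Section 5.1.3 says BAPE patients are routinely followed in pleural clinics, which limits loss, although it does not say where. A reader might also infer that the error could never be corrected. The data are linked anonymised, so sites could return to the records, at the cost of abstracting them twice.

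On size, f is assumed, and both 20% scenarios lie within the sampling interval. The synopsis ties an unfeasible study to a rate near 4.5% (100 / 0.045, about 2,200 patients), and no scenario shown comes near that. The inference that Meso-ORIGINS would be wrongly abandoned is therefore not supported.

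Finally, an estimator can be left to a statistical analysis plan. Here, however, section 10.2.2 fixes the crude proportion and section 8 lists the fields, and an analysis plan cannot use dates that were never abstracted.

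**Conclusion.** The point holds as a conditional one. The protocol leaves completed follow-up undefined, names only the centres' own sources for the outcome, and lists no item that would show how long a patient was known to be MPM-free. On the elapsed-time reading, which section 6.4 favours but does not prove, missed diagnoses can only lower the rate. On the observed reading, the rate is biased if loss is related to MPM.

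The size cannot be derived from the documents. Under the stated assumptions, 20% loss lowers a true 12% by 1.2 points (uniform departure) to 2.4 points (immediate departure). That is less than sampling error at 300 patients. Unlike sampling error, on the elapsed-time reading it acts in one direction, does not shrink with more cases and does not appear in the confidence interval. This makes it a worthwhile, inexpensive improvement and not a fatal flaw.

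**What to change.** - **Sections 6.2, 6.4 and 8, and the synopsis criteria:** define retrospective eligibility as 2 years elapsed since the BAPE diagnosis, whether or not the patient was observed throughout. Without this change there would be almost nobody to censor.
- **Section 8, Follow-up Data:** record MPM status as yes, no or not known; the date of MPM diagnosis; the date MPM-free status was last documented in any record the site can see, including letters from other hospitals; and the date of death with whether MPM was recorded.
- **Section 10.2.2, with section 4.5.2 and the synopsis end-point:** report the 2-year cumulative incidence, censoring at the last documented MPM-free date and treating death without MPM as a competing event. Give the crude proportion alongside, and state the assumption that loss is unrelated to MPM.
- **Section 6.6:** say that the procedure databases protect case finding, not outcome ascertainment.

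The cost is a few more spreadsheet columns, a little more abstraction time per case and a slightly wider interval.
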